**“Metabolism of 0.35mg Norethindrone vs 5mg
Norethindrone Acetate”**

NCT05294341

7/09/2024

Background:

Norethindrone has an elimination half-life of about 8 hours. Norethindrone acetate has an initial disappearance with half life of 7.5 minutes, with subsequent elimination half-life of 51.5 hours. Singh et. al. demonstrated that equilibrium was reached between NET and NETA 24-48 hours. Prior to 24 hours, norethindrone predominates. After 72 hours, norethindrone acetate predominates. This study suggested that the prolonged half life of norethindrone acetate contributes to prolonged action of norethindrone acetate

Study Objectives:

Specific Aim 1: To assess the relative bioavailability of norethindrone in individuals taking 5mg norethindrone acetate vs 0.35mg norethindrone

Specific Aim 2: To assess the maximum and minimum norethindrone concentrations in individuals taking 5mg norethindrone acetate vs 0.35mg norethindrone

Specific Aim 3: To assess the differences in serum levels of estradiol, LH, FSH, and progesterone levels in individuals taking 0.35mg norethindrone vs 5mg norethindrone acetate

Hypothesis: The relative bioavailability of norethindrone will be comparable in individuals taking 5mg norethindrone acetate vs 0.35mg norethindrone.

Design:

We will collect patient serum samples over the course of a week to assess for amount of norethindrone in their blood. We will also examine estradiol, follicle stimulating hormone, luteinizing hormone, and progesterone levels at various timepoints in the study. We will have patients fill out a symptom diary to document bleeding profile and side effects from their medications. This symptom diary will also have patients demonstrate satisfaction on their therapy.

Subjects in each group will be assigned either 0.35mg norethindrone or 5 mg norethindrone acetate as their initial therapy. They will start taking either medication on day 1 of their menstrual cycle. Serum levels will be drawn at 8 am for 7 days. On day 8 they will stop taking norethindrone, and will have their serum levels drawn hourly for 8 hours. They will then undergo a 1 month washout. They will do the above with the opposite therapy.

The blood draws will take place in the Clinical Research Center on the 4th floor. The samples will be stored in the Clinical Research Center freezers. [name] will then analyze the amount of norethindrone there is in each assay.

Methods:

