Statistical Analysis Plan

Serum Levels of norethindrone were averaged across all subjects on days 1 through 7. This was done for individuals taking both 5mg norethindrone acetate and 0.35mg norethindrone. Standard deviations for each of these averages were calculated. Serum levels of norethindrone were then averaged across all subjects on hours 0-8 on day 8 of the study. This was done for individuals taking both 5mg norethidnrone acetate and 0.35mg norethindrone. Standard deviations for each of these averages were calculated.

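### The SAP stops at by-drug norethindrone means and SDs: the hormone aim has no analysis, and Aims 1 and 2 have no between-drug estimate, no use of the pairing and no per-subject maximum or minimum

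*Combined protocol and SAP*

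**What the plan says.** The Study Objectives section sets three comparative aims:

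- Aim 1: "To assess the relative bioavailability of norethindrone in individuals taking 5mg norethindrone acetate vs 0.35mg norethindrone".
- Aim 2: "To assess the maximum and minimum norethindrone concentrations in individuals taking 5mg norethindrone acetate vs 0.35mg norethindrone".
- Aim 3: "To assess the differences in serum levels of estradiol, LH, FSH, and progesterone levels in individuals taking 0.35mg norethindrone vs 5mg norethindrone acetate".

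The hypothesis is also comparative: "The relative bioavailability of norethindrone will be comparable in individuals taking 5mg norethindrone acetate vs 0.35mg norethindrone". No margin or criterion for comparability is given.

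The Design section and the Methods (Study Design) both describe a two-period crossover. Each subject takes one drug for a week, has hourly draws on day 8, washes out for a month and repeats the sequence on the other drug. The four hormones are drawn on days 1, 8 and 21 of each phase.

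The Statistical Analysis Plan is one paragraph of six sentences. It averages norethindrone across subjects on days 1 to 7 for each drug. It then does the same for the day-8 profile: "Serum levels of norethindrone were then averaged across all subjects on hours 0-8 on day 8 of the study". After each step it adds: "Standard deviations for each of these averages were calculated". Nothing else is planned there. The rest of the document covers conduct and the norethindrone assay, and supplies no further analysis.

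**The concern.** The aims ask how the drugs differ, and the plan describes each drug separately.

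- **Aim 3** is not mentioned in the SAP. The samples are scheduled, but no summary of any hormone is planned, even a descriptive one.
- **Aim 1** needs a between-drug quantity. No ratio, difference, exposure measure such as AUC, or interval is named.
- **Aim 2** needs each subject's highest and lowest concentration. The plan gives only a mean profile, and the peak or trough of a mean profile is a different quantity.
- **The pairing** is the main statistical asset of a crossover, and it is discarded. The spread of each drug's values says nothing about how strongly a subject's two values move together, so the precision of the within-subject contrast cannot be recovered from the planned output.

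At stake is whether the report can answer its own aims, and whether comparability might be asserted by eye from two mean curves with SDs.

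**Working it through.** **Step 1. Set aims against data and plan.**

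| Aim | Quantity needed | Data collected | SAP output |
|---|---|---|---|
| 1 | NETA versus NET exposure | Daily samples on days 1–7; hourly on day 8; both phases | By-drug mean and SD |
| 2 | Per-subject maximum and minimum, compared | As above | By-drug mean and SD at sampled times |
| 3 | Between-drug hormone differences | Days 1, 8 and 21 of both phases | None |

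Hormone values per subject: 4 hormones × 3 days × 2 phases = 24, with 0 analyses planned. Between-drug contrasts planned for any measure: 0. These counts come from the documents and need no assumption.

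**Step 2. Why the mean profile does not serve Aim 2.** At every time point, each subject's value is at most that subject's own maximum. Averaging over subjects, the mean profile can nowhere exceed the mean of the individual maxima. Likewise it cannot fall below the mean of the individual minima. If subjects peak at different times, the planned output understates the first and overstates the second.

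**Step 3. Why by-drug SDs do not give paired precision.** With n subjects, SDs s₁ and s₂, and within-subject correlation ρ,

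var(mean difference) = (s₁² + s₂² − 2ρs₁s₂)/n.

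The SAP yields s₁ and s₂ but not ρ. With equal SDs, SE(paired)/SE(unpaired) = √(1 − ρ), which is 0.84, 0.71, 0.55 and 0.32 at assumed ρ of 0.3, 0.5, 0.7 and 0.9.

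**Step 4. Illustration only.** The documents state no n, CV or ρ. Assume n = 10 and a between-subject CV of 40%, so σ = √ln(1 + 0.4²) = √ln(1.16) = 0.385 on the log scale. The 90% CI is the ratio multiplied and divided by:

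- Unpaired: exp(t₀.₉₅,₁₈ × σ × √(2/n)) = exp(1.734 × 0.385 × 0.447) = 1.35.
- Paired with a period term (n − 2 = 8 df): exp(1.860 × σ × √(2(1 − ρ)/n)) = 1.38, 1.31, 1.25, 1.19 and 1.11 at ρ = 0, 0.3, 0.5, 0.7 and 0.9.
- Bound for any ρ, using SE ≤ 2σ/√n with 9 df: exp(1.833 × 2 × 0.385/√10) = 1.56. This needs log-scale SDs, which the SAP does not plan.

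Pairing costs degrees of freedom, so at low ρ it does not narrow the interval. Break-even ρ = 1 − (t₀.₉₅,₂ₙ₋₂ / t₀.₉₅,df)²:

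| n | Period term fitted (n − 2 df) | Plain paired (n − 1 df) |
|---|---|---|
| 6 | 0.28 | 0.19 |
| 10 | 0.13 | 0.11 |
| 20 | 0.05 | 0.05 |

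**Step 5. What the day-8 window can be called.** The Background gives "Norethindrone has an elimination half-life of about 8 hours" and "Norethindrone acetate has an initial disappearance with half life of 7.5 minutes, with subsequent elimination half-life of 51.5 hours". The assay section measures norethindrone only. Assume simple exponential decline with half-life h and no dose on day 8. Hours 0–8 then hold (2^(−24/h) − 2^(−32/h))/(1 − 2^(−24/h)) of a 24 h AUC:

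- h = 8: (0.125 − 0.0625)/0.875 = 0.071.
- h = 51.5: 0.268.

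Equal 24 h AUCs would then show a window ratio of 3.75. With a dose at hour 0 the shares are 0.571 and 0.370, a ratio of 0.65. If norethindrone declines with an 8 h half-life after both drugs, the ratio is 1.0. Because 51.5 h is stated for the acetate and not for norethindrone, these figures show only that the label matters. They do not estimate a bias.

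**Step 6. Is pairing blocked by carryover?** A washout of 28–30 days is 13.0–14.0 half-lives at 51.5 h, leaving about 0.01% of drug. Drug carryover is therefore no obstacle. This says nothing about hormonal or cycle carryover.

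**The case against.** The Methods call this a pilot without randomisation, and the SAP is in the past tense, so it reads as an account of analyses already done. By-drug means with SDs are a recognised pilot output. A reader could divide one mean by the other and, knowing n, attach a conservative interval.

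Much of this stands for Aims 1 and 2. A pilot owes no powered test, and a crude ratio is available to anyone who computes it. But that ratio is unplanned, carries no within-subject precision and does not provide Aim 2's maxima and minima. For Aim 3 the objection fails, because descriptive reporting is missing too.

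A reader might also infer more than the documents support:

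- **That pairing would narrow the intervals by a known amount.** No n, CV or correlation is given, and at low correlation pairing gains nothing. The widths above are illustration.
- **That the day-8 comparison is distorted 3.75-fold.** That figure applies the acetate's half-life to norethindrone, which the documents do not do.
- **That the hormones were never assayed.** Only a norethindrone assay is described, but that silence does not show that hormone results are absent.

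**Conclusion.** The concern holds as an omission from the analysis plan, and it needs correcting before results are interpreted. Aim 3 is the strongest part: 24 scheduled values per subject and no analysis. For Aims 1 and 2 the plan gives no between-drug estimate, no use of the pairing and no per-subject maximum or minimum.

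This conclusion rests on the text alone and on no assumed number. The size of the precision loss for this trial is unknown and cannot be derived from the documents. The documents also do not support reading the day-8 values as Cmax, Cmin or relative bioavailability. Both the Design section and the Methods say dosing stopped on day 8, but the time from last dose to hour 0 has to come from study records.

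**What to change.** 1. **Aim 3.** For each hormone, choose one scale (difference or log-scale ratio) and report the paired between-drug contrast with a 95% CI at day 8. Do the same at day 21, labelled off-drug. If days count from the first dose, day 21 falls 13–14 days after the last one. Adjust for day 1 only if that sample preceded the first dose. State that drug washout does not exclude hormonal or cycle carryover. If the hormones were not assayed, report Aim 3 as not analysed.

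2. **Aims 1 and 2.** For each subject and phase, derive the 0–8 h AUC and the highest and lowest concentration within the day-8 window only. Do not pool these with the single daily samples of days 1–7, which the Methods place within an hour of dosing. Report within-subject log-scale NETA/NET geometric mean ratios with CIs at a stated level, from a paired analysis with a period term if n allows. Give them as measured, and also dose-normalised by labelled mass (5/0.35 = 14.3), noting that this is not norethindrone-equivalent.

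3. **Labels.** Call these observed exposure in the day-8 window. Use Cmax, Cmin or relative bioavailability only if records show when the last dose was taken relative to hour 0 and the window supports those terms.

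4. **Claims.** Make no comparability claim without a margin set before results were seen. Label the analyses post hoc if results were already known. Keep the mean and SD profiles as description.

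**Cost.** SAP wording, a check of dosing and draw times in the records, and a short re-analysis of samples already in the plan. Hormone assays are an added cost only if they were not run and Aim 3 is to be kept. Intervals will probably be wide, and relative bioavailability over a full dosing interval may not be recoverable from this sampling.
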